**Comorbidities/Symptoms**

- History of All-Cause Hospitalization
- History of Emergency Department Visit
- History of Hospitalization due to Respiratory Condition
- Acute Myocardial Infarction
- Angina Pectoris
- Peripheral Vascular Disease
- Heart Failure
- Hypertension
- Upper Respiratory Infection
- Lower Respiratory Infection
- Cardiac Arrhythmias
- Cerebrovascular Disease
- All Cancers (except nonmelanoma skin cancer)
- Allergic Rhinitis
- Chronic Sinusitis
- Bronchiectasis
- Pneumonia
- Chronic Bronchitis
- Exertional Breathlessness
- Anxiety
- Dementia
- Depression
- Osteoporosis
- Charlson Deyo Comorbidity Index
- Acute Liver Injury or Failure
- Chronic Kidney Disease (without ESRD)
- End Stage Renal Disease
- Rheumatic Disease
- Peptic Ulcer Disease
- Gastroesophageal Reflux Disease
- Type 1 Diabetes Mellitus
- Type 2 Diabetes Mellitus
- HIV/AIDS
- Hemiplegia or Paraplegia

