Acute Myocardial Infarction	
1 Inpatient or 1 Outpatient
 
Diagnosis Code (Position 1), ICD-9 is any of: { “410”, “410.0”, “410.00”, “410.01”, “410.1”, “410.10”, “410.11”, “410.2”, “410.20”, “410.21”, “410.3”, “410.30”, “410.31”, “410.4”, “410.40”, “410.41”, “410.5”, “410.50”, “410.51”, “410.6”, “410.60”, “410.61”, “410.7”, “410.70”, “410.71”, “410.8”, “410.80”, “410.81”, “410.9”, “410.90”, “410.91” }
 
Diagnosis Code (Principal), ICD-10 is any of: { “I21.09”, “I21.11”, “I21.19”, “I21.29”, “I21.3”, “I21.4”, “I22.0”, “I22.1”, “I22.2”, “I22.8”, “I22.9” }

Angina Pectoris	
1 Inpatient or 2 Outpatient (30 – 365 days apart)
 
Diagnosis Code (Any Position), ICD-9 is any of: { “413”, “413.0”, “413.1”, “413.9” }
 
Diagnosis Code (Any Position), ICD-10 is any of: { “I20.1”, “I20.8”, “I20.9” }

Peripheral Vascular Disease	
1 Inpatient or 2 Outpatient (30 – 365 days apart)
 
Diagnosis Code (Any Position), ICD-9 is any of: { “440”, “440.0”, “440.1”, “440.2”, “440.20”, “440.21”, “440.22”, “440.23”, “440.24”, “440.29”, “440.3”, “440.30”, “440.31”, “440.32”, “440.4”, “440.8”, “440.9”, “441”, “441.0”, “441.00”, “441.01”, “441.02”, “441.03”, “441.1”, “441.2”, “441.3”, “441.4”, “441.5”, “441.6”, “441.7”, “441.9”, “442”, “442.0”, “442.1”, “442.2”, “442.3”, “442.8”, “442.81”, “442.82”, “442.83”, “442.84”, “442.89”, “442.9”, “443.1”, “443.2”, “443.21”, “443.22”, “443.23”, “443.24”, “443.29”, “443.8”, “443.81”, “443.82”, “443.89”, “443.9”, “447.1”, “785.4”, “38.13”, “38.14”, “38.16”, “38.18”, “38.33”, “38.34”, “38.36”, “38.38”, “38.43”, “38.44”, “38.46”, “38.48”, “39.22”, “39.23”, “39.24”, “39.25”, “39.26”, “39.29” }
 
Diagnosis Code (Any Position), ICD-10 is any of: { “I70.0”, “I70.1”, “I70.209”, “I70.219”, “I70.229”, “I70.25”, “I70.269”, “I70.299”, “I70.399”, “I70.499”, “I70.599”, “I70.8”, “I70.90”, “I70.91”, “I70.92”, “I71.00”, “I71.01”, “I71.02”, “I71.03”, “I71.1”, “I71.2”, “I71.3”, “I71.4”, “I71.5”, “I71.6”, “I71.8”, “I71.9”, “I72.0”, “I72.1”, “I72.2”, “I72.3”, “I72.4”, “I72.8”, “I72.9”, “I73.1”, “I73.81”, “I73.89”, “I73.9”, “I77.1”, “I77.71”, “I77.72”, “I77.73”, “I77.74”, “I77.79”, “I79.8”, “I96” }

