Heart Failure	
1 Inpatient
 
Diagnosis Code (Any Position), ICD-9 is any of: { “428”, “428.0”, “428.1”, “428.2”, “428.20”, “428.21”, “428.22”, “428.23”, “428.3”, “428.30”, “428.31”, “428.32”, “428.33”, “428.4”, “428.40”, “428.41”, “428.42”, “428.43”, “428.9” }
 
Diagnosis Code (Any Position), ICD-10 is any of: { “I50”, “I50.9”, “I50.2”, “I50.20”, “I50.21”, “I50.22”, “I50.23”, “I50.3”, “I50.30”, “I50.31”, “I50.32”, “I50.33”, “I50.4”, “I50.40”, “I50.41”, “I50.42”, “I50.43” }

Hypertension	
1 Inpatient or 2 Outpatient (30 – 365 days apart)
 
Diagnosis Code (Any Position), ICD-9 is any of: { “401”, “401.0”, “401.1”, “401.9”, “402”, “402.0”, “402.00”, “402.1”, “402.10”, “402.9”, “402.90”, “403”, “403.0”, “403.00”, “403.01”, “403.1”, “403.10”, “403.11”, “403.9”, “403.90”, “403.91”, “404”, “404.0”, “404.00”, “404.01”, “404.02”, “404.03”, “404.1”, “404.10”, “404.11”, “404.12”, “404.13”, “404.9”, “404.90”, “404.91”, “404.92”, “404.93”, “405”, “405.0”, “405.01”, “405.09”, “405.1”, “405.11”, “405.19”, “405.9”, “405.91”, “405.99” }
 
Diagnosis Code (Any Position), ICD-10 is any of: { “I10”, “I11.9”, “I12.0”, “I12.9”, “I13.0”, “I13.10”, “I13.11”, “I13.2”, “I15.0”, “I15.8” }

Upper Respiratory Infection (with no sinusitis)	
1 Inpatient or 2 Outpatient (30 – 365 days apart)
 
Diagnosis Code (Any Position), ICD-9 is any of: { “034”, “034.0”, “034.1”, “460”, “461”, “461.0”, “461.1”, “461.2”, “461.3”, “461.8”, “461.9”, “462”, “463”, “464”, “464.0”, “464.00”, “464.01”, “464.1”, “464.10”, “464.11”, “464.2”, “464.20”, “464.21”, “464.3”, “464.30”, “464.31”, “464.4”, “464.5”, “464.50”, “464.51”, “465”, “465.0”, “465.8”, “465.9”, “487”, “487.1”, “487.8” }
 
Diagnosis Code (Any Position), ICD-10 is any of: { “J03.00”, “J03.01”, “A38”, “A38.8”, “A38.9”, “J00”, “J01”, “J01.9”, “J01.90”, “J01.8”, “J01.80”, “J01.0”, “J01.00”, “J01.01”, “J32.0”, “J01.1”, “J01.10”, “J01.11”, “J32.1”, “J01.2”, “J01.20”, “J01.21”, “J32.2”, “J01.3”, “J01.30”, “J01.31”, “J32.3”, “J02”, “J02.8”, “J02.9”, “J04”, “J04.0”, “J05”, “J05.0”, “J04.1”, “J04.10”, “J04.11”, “J04.2”, “J05.1”, “J05.10”, “J05.11”, “J04.3”, “J04.30”, “J04.31”, “J06”, “J06.9”, “J11.89”, “J11.8”, “J11.1”, “J11”, “J10.89”, “J10.8”, “J10.1”, “J10.00”, “J10.0”, “J10”, “J09.X2”, “J09.X9”, }

	“J09.X”, “J09” }

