Lower Respiratory Infection	
1 Inpatient or 2 Outpatient (30 – 365 days apart)
 
Diagnosis Code (Any Position), ICD-9 is any of: { “466”, “466.0”, “466.1”, “466.11”, “466.19” }
 
Diagnosis Code (Any Position), ICD-10 is any of: { “J20.9”, “J21.0”, “J21.8”, “J22” }

Cardiac Arrhythmias	
1 Inpatient or 1 Outpatient
 
Diagnosis Code (Principal), ICD-9 is any of: { “427”, “427.0”, “427.1”, “427.2”, “427.3”, “427.31”, “427.32”, “427.4”, “427.41”, “427.42”, “427.5”, “427.6”, “427.60”, “427.61”, “427.69”, “427.8”, “427.81”, “427.89”, “427.9” }
 
Diagnosis Code (Position 1), ICD-10 is any of: { “I46.9”, “I47.1”, “I47.2”, “I47.9”, “I48.91”, “I48.92”, “I49.01”, “I49.02”, “I49.1”, “I49.3”, “I49.40”, “I49.49”, “I49.5”, “I49.8”, “I49.9”, “R00.1” }

Cerebrovascular Disease	
1 Inpatient
 
Diagnosis Code (Any Position), ICD-9 is any of: { “430”, “431”, “432”, “432.0”, “432.1”, “432.9”, “433”, “433.0”, “433.01”, “433.1”, “433.11”, “433.2”, “433.21”, “433.3”, “433.31”, “433.8”, “433.81”, “433.9”, “433.91”, “434”, “434.0”, “434.01”, “434.1”, “434.11”, “434.9”, “434.90”, “434.91”, “435”, “435.8”, “435.9”, “436” }
 
Diagnosis Code (Any Position), ICD-10 is any of: { “G45”, “G45.8”, “G45.9”, “I60”, “I60.0”, “I60.00”, “I60.01”, “I60.02”, “I60.1”, “I60.10”, “I60.11”, “I60.12”, “I60.2”, “I60.20”, “I60.21”, “I60.22”, “I60.3”, “I60.30”, “I60.31”, “I60.32”, “I60.4”, “I60.5”, “I60.50”, “I60.51”, “I60.52”, “I60.6”, “I60.7”, “I60.8”, “I60.9”, “I61”, “I61.0”, “I61.1”, “I61.2”, “I61.3”, “I61.4”, “I61.5”, “I61.6”, “I61.8”, “I61.9”, “I62”, “I62.0”, “I62.00”, “I62.01”, “I62.02”, “I62.03”, “I62.1”, “I62.9”, “I63”, “I63.0”, “I63.00”, “I63.01”, “I63.011”, “I63.012”, “I63.019”, “I63.02”, “I63.03”, “I63.031”, “I63.032”, “I63.039”, “I63.09”, “I63.1”, “I63.10”, “I63.11”, “I63.111”, “I63.112”, “I63.119”, “I63.12”, “I63.13”, “I63.131”, “I63.132”, “I63.139”, “I63.19”, “I63.2”, “I63.20”, “I63.21”, “I63.211”, “I63.212”, “I63.219”, “I63.22”, “I63.23”, “I63.231”, “I63.232”, “I63.239”, “I63.29”, “I63.3”, “I63.30”, “I63.31”, “I63.311”, “I63.312”, “I63.319”, “I63.32”, “I63.321”, “I63.322”, “I63.329”, “I63.33”, “I63.331”, “I63.332”, “I63.339”, “I63.34”, “I63.341”, “I63.342”, “I63.349”, “I63.39”, “I63.4”, “I63.40”, “I63.41”, “I63.411”, “I63.412”, “I63.419”, “I63.42”, “I63.421”, “I63.422”, “I63.423” }

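### Annex 4: the ICD-10 code list for Cardiac Arrhythmias is narrower than its ICD-9 counterpart, so the covariate is incomplete for atrial fibrillation and flutter

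*Combined protocol and SAP*

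**What the plan says.** Section 9.3.3 lists "Cardiac Arrhythmias" among the comorbidities. It is not one of the components of the Charlson-Deyo index in Annex 4. It is therefore not removed by the rule that drops those components, and it enters three models as its own term: the propensity score (section 9.2.2, Matched Cohort) and the multivariable Cox and logistic models in the unmatched cohort (section 9.7.1.3). It also has a row in Tables 2 and 3 of Annex 5.

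Annex 4 defines the measure by "1 Inpatient or 1 Outpatient" claim, with two lists:

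- The ICD-9 list is headed "Diagnosis Code (Principal), ICD-9". It has 19 codes from the 427 family. These include the parents 427 and 427.3 and, for the relevant part, "427.3”, “427.31”, “427.32".
- The ICD-10 list is headed "Diagnosis Code (Position 1), ICD-10". It has 16 exact codes, of which the first ten are "I46.9”, “I47.1”, “I47.2”, “I47.9”, “I48.91”, “I48.92”, “I49.01”, “I49.02”, “I49.1”, “I49.3". The remaining six are I49.40, I49.49, I49.5, I49.8, I49.9 and R00.1.

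The plan gives no reason for the difference between the lists or between the field labels.

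**The concern.** The two lists are meant to measure one condition, but they are built differently. The ICD-9 side lists 427.3 and both of its subcodes. The ICD-10 side holds two I48 codes and nothing else from that category. A wildcard cannot be read in, because Annex 4 writes wildcards and parents where it wants them: R06.0* for exertional breathlessness, O98.7* for HIV/AIDS, and I50 with its subcodes for heart failure.

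Two uses of the flag are affected. Describing new users before and after matching is a stated secondary objective (section 8), and Table 2 would show too little arrhythmia. Section 9.12 presents the covariates as hypothesised confounders. A small standardised difference in Table 3 for an incomplete flag would reassure more than it should about balance on the condition itself.

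**Working it through.** **1. List comparison.** Of the 16 ICD-10 codes, 2 fall in I48 (I48.91 and I48.92). The documents print no code descriptions. That other I48 codes exist for fibrillation and flutter, and that I47.0 and I49.2 belong with the 427 family, is taken from the classification as an assumption. The asymmetry itself (a parent and its subcodes on one side, two isolated codes on the other) is visible in Annex 4.

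**2. How much baseline time rests on the ICD-10 list.** Comorbidities are sought in the 180 days before entry (section 9.7.1.1). Entry runs from 17 November 2015 to 31 March 2018, which is 866 days. The first baseline starts on 21 May 2015 (section 9.2.1). Assume that ICD-10 applies from 1 October 2015 and that entry is uniform.

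- The first entrant has 133 baseline days under ICD-9 (21 May to 30 September 2015). The number falls by one for each later entry day.
- Entry days with any ICD-9 baseline: 133 / 866 = 15.4%.
- ICD-9 baseline days: 133 × 134 / 2 = 8,911. All baseline days: 866 × 180 = 155,880. Share: 8,911 / 155,880 = 5.7%.
- The ICD-10 list therefore governs about 94% of baseline time.

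In sensitivity analysis 3, entry starts on 21 May 2015, so the earliest entrants have a wholly ICD-9 baseline. The covariate there does not mean quite what it means in the main cohort.

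**3. Share of patients with fibrillation or flutter who are missed.** The plan gives no coding frequencies. Let u be the share with at least one I48.91 or I48.92 claim in the 180 days, and f the share of those with at least one such claim first-listed. Then missed = 1 − u × f. Both ranges are assumed.

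| u | f = 0.9 | f = 0.3 |
|---|---|---|
| 0.3 | 73% | 91% |
| 0.5 | 55% | 85% |
| 0.7 | 37% | 79% |
| 0.9 | 19% | 73% |

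The range is 19% to 91%. It combines the short list with the first-position limit. With the position limit set aside (f = 1), the list alone gives 1 − u, that is 10% to 70% for the same values of u. These are upper figures for each u and f, since some patients would be flagged by another listed arrhythmia code.

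**4. Worst case for the hazard ratio.** Suppose that the flag captures nothing and that no other covariate compensates. With arrhythmia prevalence pA and pB in the two arms, and hazard ratio r of arrhythmia on discontinuation, the bias factor is (1 + pA(r − 1)) / (1 + pB(r − 1)). All inputs are assumed.

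- 20% v 15%: r = 1.1 gives 1.020 / 1.015 = 1.005; r = 1.5 gives 1.100 / 1.075 = 1.023.
- 15% v 13%: r = 1.1 gives 1.015 / 1.013 = 1.002; r = 1.5 gives 1.075 / 1.065 = 1.009.
- Equal prevalence: 1.000 for any r.

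The largest value is about 2%.

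**The case against.** The strongest reply is that little depends on this. One list applies to both arms for about 94% of baseline time, entry year is in the propensity score, and nothing in the documents suggests that arrhythmia or its coding differs between the products. The score also contains anticoagulants, antihypertensives, all-cause hospitalisation and the Charlson-Deyo index, which should take up part of any imbalance in arrhythmia. Section 9.9 already acknowledges residual confounding. All of this stands, and it is why the point concerns measurement and description more than the primary estimate.

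A second reply is that the first-position rule is deliberate. It applies to both coding systems, so it is not an ICD-10 fault. The neighbouring conditions that accept "Diagnosis Code (Any Position), ICD-10" generally ask for more: hypertension, angina and peripheral vascular disease need one inpatient claim or two outpatient claims 30 to 365 days apart, and heart failure needs an inpatient claim. Arrhythmia needs one outpatient claim. A stricter position with fewer claims is a recognisable trade of sensitivity for specificity. This also stands, so the position rule as such is not counted as an error here.

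A third reply is procedural. Section 9.12 promises medical review of code lists before implementation, and section 9.8 allows measure definitions to change by documented amendment. These give a route for correction, but they do not correct the list as printed.

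**Conclusion.** The mismatch is real and unexplained. Followed as written, the definition under-captures fibrillation and flutter in the ICD-10 era, which is most of the baseline time. Table 2 would understate arrhythmia, and matching would balance an incomplete flag. The extent is unknown, and the effect on the primary hazard ratio is probably small. Both ranges above rest on assumed inputs, and the 94% rests on the assumed switch date and uniform entry. The change is worth making because it costs little and improves a named confounder and a descriptive objective.

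Three stronger conclusions might be inferred, and the documents support none of them.

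- That most patients with fibrillation are missed: this needs coding frequencies that the plan does not give, and a single first-listed I48.91 or I48.92 claim in 180 days is enough to be captured.
- That the comparison between products is materially biased: no difference between arms is shown, and even the worst case above is about 2%.
- That the Acute Myocardial Infarction list needs the same rewrite: its field labels are the reverse of those for arrhythmia (Position 1 for ICD-9, Principal for ICD-10), but no missing code has been identified there. As a Charlson component it is not a separate term in the propensity score.

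**What to change.** In Annex 4, Cardiac Arrhythmias:

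1. Replace I48.91 and I48.92 with I48.*, and add I47.0 and I49.2, so that the ICD-10 list matches the 427 family. The medical code-list review promised in section 9.12 should confirm the mapping. If the narrow list is intended, state why.
2. Use one field label for both coding systems in place of the present mix of Principal and Position 1.
3. Fit the propensity score, the match and Tables 2 and 3 with the corrected flag.

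Any-position capture should be at most a descriptive check, for example an extra prevalence figure beside Table 2. On a single outpatient claim it would gain sensitivity but lose specificity.

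The cost is a code-list edit recorded as an amendment under section 9.8. The milestones in section 6 precede the protocol date, so result tables may already exist. If they do, the cost also includes refitting the score, rematching, and rerunning the analyses that use the flag or the matched cohort.

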### **9.2 SETTING**

#### **9.2.1 Definitions**

Study Period: the period of time that includes the exclusion criteria assessment period, baseline, cohort entry date, and follow-up period for the study population. This period is the same for all patients.

The study period will be from 1 January 2008 to 31 March 2018, encompassing date of the earliest data availability to the date of the latest data availability.

Patient Selection Period: the period of time for which patients are eligible to enter the cohort. The earliest date of the patient selection period is 17 November 2015, corresponding to 180-days after US approval date of Stiolto Respimat.

Cohort Entry Date: Date of entry to the initial cohort of Stiolto or Anoro users.

[figure not shown]
Baseline Period: the 180-day period that ends 1 day prior to the cohort entry date used to assess covariate information. The baseline period will vary between patients depending on these dates. The earliest start of the baseline period would be 21 May 2015, the date of Stiolto approval (i.e. 180 days before November 17, 2015).

Follow-Up Period: the period of time between 1 day after the cohort entry date to the earliest occurrence of the outcome (discontinuation of refills), or any censoring criteria (365 days, death, disenrollment, or end of data). Addition of another treatment in addition to index treatment will not count as discontinuation.

For entry into the study population, patients will be required to have 180 days of continuous enrolment with both medical and pharmacy coverage. Data during the baseline period will be used to confirm study eligibility and classification of incident COPD. The follow-up period will be used for capturing first and second maintenance therapies. This is illustrated in **Figure 1**.

Figure 1

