## Study timeline for the Primary Study Population

## 9.2.2 Study population

The pre-matched study cohort will consist of patients initiating Olodaterol/Tiotropium Bromide or Umeclidinium/Vilanterol between 17 November 2015 and 31 March 2018.

The following exclusion criteria will then be applied:

Aged <40 years.

Enrolment with medical and pharmacy coverage prior to the cohort entry < 180 days.

Never had COPD diagnosis on the cohort entry date or prior to cohort entry.

A record for dispensed Olodaterol/Tiotropium Bromide delivered with Respimat inhalator or Umeclidinium/Vilanterol delivered with the Ellipta Inhaler during the 180-day baseline prior to cohort entry.

[figure not shown]
Diagnosis of asthma any time prior to cohort entry.

Diagnosis of lung cancer any time prior to cohort entry.

Diagnosis of lung transplant any time prior to cohort entry.

Figure 2

Below depicts the flow diagram of patients.

Diagnosis of COPD (ICD-9: 491.\*, 492.\*, 496.\*; ICD-10: J41.0, J41.1, J41.8, J42.\*, J43.0, J43.1, J43.2, J43.8, J43.9, J44.0, J44.1, J44.9) will be defined as the presence of an inpatient or outpatient claim.

Diagnosis of asthma (ICD-9: 493.\*; ICD-10: J45, J45.20, J45.21, J45.22, J45.90\*, J45.99\*) will be defined as either 1 inpatient claim or 2 outpatient events 30-365 days apart.

Diagnosis of lung cancer (ICD-9: 162.2, 162.3, 162.4, 162.5, 162.8, 162.9, 231.2; ICD-10: C34.00, C34.01, C34.02, C34.10, C34.11, C34.12, C34.2, C34.30, C34.31, C34.32, C34.80, C34.81, C34.82, C34.90, C34.91, C34.92, C7A.090, D02.20, D02.21, D02.22, Z85.118) will be defined as either 1 inpatient claim or 2 outpatient events 30-365 days apart.

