#### 9.7.1.1 Descriptive Analysis

All variables specified in [section 9.3.3](#) will be reported. For demographic and lifestyle variables, the value recorded on the cohort entry date will be reported, otherwise the most recent known value will be reported. Presence of comorbidities and use of concomitant medication use will be determined based whether they ever occurred within the 180-day baseline period preceding the index date. Differences in the confounder distributions were inspected for successful confounder balance of measured characteristics.

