History of Hospitalization due to Respiratory Condition	1 Inpatient 
Diagnosis Code (Principal), ICD-9 is any of: { "415.1", "415.11", "415.12", "415.13", "415.19", "465", "465.0", "465.8", "465.9", "466", "466.0", "466.1", "466.11", "466.19", "480.0", "480.1", "480.2", "480.3", "480.8", "480.9", "481", "482.0", "482.1", "482.2", "482.30", "482.31", "482.32", "482.39", "482.40", "482.41", "482.42", "483.0", "483.1", "483.8", "484.1", "484.3", "484.5", "484.6", "484.7", "484.8", "486", "487.0", "488.01", "488.11", "488.81", "490", "491", "491.0", "491.1", "491.2", "491.20", "491.21", "491.22", "491.8", "491.9", "492.0", "492.8", "493.0", "493.00", "493.01", "493.02", "493.1", "493.10", "493.11", "493.12", "496", "515", "516.3", "516.30", "516.31", "516.32", "516.8", "516.9", "518.81", "518.83", "518.84" }
 
Diagnosis Code (Principal), ICD-10 is any of: { "A01.03", "A02.22", "A37.01", "A37.11", "A37.81", "A37.91", "A40.3", "A50.04", "A54.84", "B01.2", "B05.2", "B06.81", "B77.81", "B95.3", "B96.0", "B96.1", "I26.9", "I26.90", "I26.92", "I26.99", "J06", "J06.0", "J06.9", "J09.X1", "J09.X2", "J10.0", "J10.00", "J10.01", "J10.08", "J10.1", "J11.0", "J11.00", "J11.08", "J11.1", "J12", "J12.0", "J12.1", "J12.2", "J12.3", "J12.8", "J12.81", "J12.89", "J12.9", "J13", "J14", "J15", "J15.0", "J15.1", "J15.2", "J15.20", "J15.21", "J15.211", "J15.212", "J15.29", "J15.3", "J15.4", "J15.5", "J15.6", "J15.7", "J15.8", "J15.9", "J16", "J16.0", "J16.8", "J17", "J18", "J18.0", "J18.1", "J18.2", "J18.8", "J18.9", "J20", "J20.0", "J20.1", "J20.2", "J20.3", "J20.4", "J20.5", "J20.6", "J20.7", "J20.8", "J20.9", "J21.0", "J22", "J39", "J39.3", "J39.8", "J39.9", "J40", "J41", "J41.0", "J41.1", "J41.8", "J42", "J43", "J43.0", "J43.1", "J43.2", "J43.8", "J43.9", "J44.0", "J45", "J45.2", "J45.20", "J45.21", "J45.22", "J45.3", "J45.30", "J45.31", "J45.32", "J45.4", "J45.40", "J45.41", "J45.42", "J45.5", "J45.50", "J45.51", "J45.52", "J45.9", "J45.90", "J45.901", "J45.902", "J45.909", "J45.99", "J45.991", "J45.998", "J47.0", "J68.0", "J84.111", "J84.116", "J84.117", "J84.2", }

	“J85.1”, “J96”, “J96.9”, “J96.90”, “J96.91”, “J96.92”, “J96.0”, “J96.00”, “J96.01”, “J96.02”, “J96.1”, “J96.10”, “J96.11”, “J96.12”, “J96.2”, “J96.20”, “J96.21”, “J96.22”, “J98”, “J98.2”, “J98.3”, “J98.8” }

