Pneumonia	
1 Inpatient or 2 Outpatient (30 – 365 days apart)
 
Diagnosis Code (Any Position), ICD-9 is any of: { “003.22”, “020.3”, “020.4”, “020.5”, “021.2”, “022.1”, “031.0”, “039.1”, “052.1”, “055.1”, “073.0”, “083.0”, “112.4”, “114.0”, “114.4”, “114.5”, “115.05”, “115.15”, “115.95”, “130.4”, “136.3”, “480.0”, “480.1”, “480.2”, “480.3”, “480.8”, “480.9”, “481”, “482”, “482.0”, “482.1”, “482.2”, “482.3”, “482.30”, “482.31”, “482.32”, “482.39”, “482.4”, “482.40”, “482.41”, “482.42”, “482.49”, “482.8”, “482.81”, “482.82”, “482.83”, “482.84”, “482.89”, “482.9”, “483”, “483.0”, “483.1”, “483.8”, “484”, “484.1”, “484.3”, “484.5”, “484.6”, “484.7”, “484.8”, “485”, “486”, “487”, “487.0”, “487.1”, “487.8”, “517.1” }
 
Diagnosis Code (Any Position), ICD-10 is any of: { “A01.03”, “A02.22”, “A20.2”, “A21.2”, “A22.1”, “A31.0”, “A37.01”, “A37.11”, “A37.91”, “A43.0”, “A49.2”, “B01.2”, “B05.2”, “B06.81”, “B25.0”, “B37.1”, “B38.0”, “B38.1”, “B38.2”, “B39.0”, “B39.1”, “B39.2”, “B44.0”, “B58.3”, “B59”, “B77.81”, “J09”, “J09.X”, “J09.X1”, “J09.X2”, “J09.X9”, “J10”, “J10.0”, “J10.00”, “J10.01”, “J10.08”, “J10.1”, “J10.8”, “J10.89”, “J11”, “J11.0”, “J11.00”, “J11.08”, “J11.8”, “J11.89”, “J12.0”, “J12.1”, “J12.2”, “J12.3”, “J12.81”, “J12.89”, “J12.9”, “J13”, “J14”, “J15.0”, “J15.1”, “J15.20”, “J15.211”, “J15.212”, “J15.29”, “J15.3”, “J15.4”, “J15.5”, “J15.6”, “J15.7”, “J15.8”, “J15.9”, “J16.0”, “J16.8”, “J17”, “J18.0”, “J18.1”, “J18.8”, “J18.9” }

Chronic Bronchitis	
1 Inpatient or 2 Outpatient (30 – 365 days apart)
 
Diagnosis Code (Any Position), ICD-9 is any of: { “491”, “491.0”, “491.1”, “491.2”, “491.20”, “491.21”, “491.22”, “491.8”, “491.9” }
 
Diagnosis Code (Any Position), ICD-10 is any of: { “J41”, “J41.0”, “J41.1”, “J41.8”, “J42” }

Exertional Breathlessness	
1 Inpatient or 2 Outpatient (30 – 365 days apart)
 
Diagnosis Code (Any Position), ICD-10 is any of: { “R06.0*” }
 
Diagnosis Code (Any Position), ICD-9 is any of: { “786.0” }

Anxiety	
1 Inpatient or 2 Outpatient (30 – 365 days apart)
 
Diagnosis Code (Any Position), ICD-9 is any of: { “293.84”, “300.0”, “300.00”, “300.02”, “300.09”, “309.21”, “309.24”, “309.28”, “313.0” }
 
Diagnosis Code (Any Position), ICD-10 is any of: { “F06.4”, “F41.1”, “F41.8”, “F41.9”, “F43.22”, “F43.23”, “F93.0”, “F93.8”, “F40”, “F40.8”, “F40.9”, “F41”, “F41.0”, “F41.3” }

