Charlson-Deyo Comorbidity Index	
This measure computes a score by summing over the following components:
 
 
· If the event Acute Myocardial Infarction Occurs within 180 days, set the score to 1.0 Otherwise, set the score to 0.0
 
· If the event Heart Failure Occurs within 180 days, set the score to 1.0 Otherwise, set the score to 0.0
 
· If the event Peripheral Vascular Disease Occurs within 180 days, set the score to 1.0 Otherwise, set the score to 0.0
 
· If the event Cerebrovascular Disease Occurs within 180 days, set the score to 1.0 Otherwise, set the score to 0.0
 
· If the event Dementia Occurs within 180 days, set the score to 1.0 Otherwise, set the score to 0.0
 
· If the event Chronic Obstructive Pulmonary Disease Occurs within 180 days, set the score to 1.0 Otherwise, set the score to 0.0
 
· If the event Rheumatologic Disease Occurs within 180 days, set the score to 1.0 Otherwise, set the score to 0.0
 
· If the event Peptic Ulcer Disease Occurs within 180 days, set the score to 1.0 Otherwise, set the score to 0.0
 
· If the event Hemiplegia or Paraplegia Occurs within 180 days, set the score to 2.0 Otherwise, set the score to 0.0
 
· If the event Renal Disease Occurs within 180 days, set the score to 2.0 Otherwise, set the score to 0.0
 
· If the event HIV/AIDS Occurs within 180 days, set the score to 6.0 Otherwise, set the score to 0.0
 
· For the measure Cancer use the value of the measure as the score multiplied by weight 1.0 If the value is missing, set the score to 0.0
 
· For the measure Diabetes use the value of the measure as the score multiplied by weight 1.0 If the value is missing, set the score to 0.0
 
· For the measure Liver Disease use the value of the measure as the score multiplied by weight 1.0 If the value is missing, set the score to 0.0
 

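### Chronic Bronchitis covers all of ICD-9 491 but only J41/J42 under ICD-10, and no diagnosis covariate captures outpatient COPD exacerbation in either coding era

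*Combined protocol and SAP*

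**What the plan says.** Annex 4 counts a patient as having Chronic Bronchitis on one inpatient claim, or on two outpatient claims 30 to 365 days apart. The ICD-9 codes are "491”, “491.0”, “491.1”, “491.2”, “491.20”, “491.21”, “491.22”, “491.8”, “491.9". The ICD-10 codes are "J41”, “J41.0”, “J41.1”, “J41.8”, “J42".

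Section 9.2.2 defines COPD for cohort entry by ICD-9 491.*, 492.* and 496.* together with twelve ICD-10 codes, ending "J43.9, J44.0, J44.1, J44.9) will be defined as the presence of an inpatient or outpatient claim".

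Section 9.7.1.1 says comorbidities are "determined based whether they ever occurred within the 180-day baseline period preceding the index date". Section 9.2.1 adds: "The earliest start of the baseline period would be 21 May 2015". Sensitivity analysis 3 (section 9.7.2) moves the start of patient identification back to 21 May 2015, so its baselines reach back further still.

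Chronic Bronchitis is listed in section 9.3.3. It therefore enters the propensity score (section 9.2.2, Matched Cohort) and the multivariable models (section 9.7.1.3). The Cox model in the matched cohort has treatment as its only term.

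**The concern.** When it selects patients, the plan groups J44 with 491. When it measures Chronic Bronchitis, it keeps 491.20 to 491.22 on the ICD-9 side and has no J44 code on the ICD-10 side. No reason is given. A patient whose qualifying claims carry 491.21 is positive, while one whose claims carry J44.1 is negative, yet both are given the same coefficient.

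The list also shows what is absent. Section 7 names fewer exacerbations as one aim of maintenance treatment, and recent exacerbation could plausibly influence both product choice and stopping. Section 9.3.3 nevertheless has no exacerbation covariate. Because the matched Cox model adjusts for nothing further, control of measured confounding rests on what the propensity score contains. Tables 2 and 3 could show good balance on Chronic Bronchitis while exacerbation history remained unbalanced.

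**Working it through.** **The plan's own date.** 17 November 2015 minus 180 days is 21 May 2015, as section 9.2.1 states.

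**Code lists side by side** (section 9.2.2 and Annex 4):

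| Measure | ICD-9 | ICD-10 J44 codes | Rule |
|---|---|---|---|
| COPD, cohort entry | 491.*, 492.*, 496.* | J44.0, J44.1, J44.9 | any inpatient or outpatient claim |
| Chronic Bronchitis | all of 491 | none | 1 inpatient, or 2 outpatient 30–365 days apart |
| Respiratory Hospitalization | includes 491.20–491.22 and 496 | J44.0 only | 1 inpatient, principal diagnosis |
| Lower Respiratory Infection | 466 codes | none | 1 inpatient, or 2 outpatient 30–365 days apart |
| Upper Respiratory Infection, Pneumonia | no 491 code | none | same |

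Of the twelve ICD-10 COPD codes in section 9.2.2, Chronic Bronchitis covers J41.0, J41.1, J41.8 and J42. It omits five J43 codes and all three J44 codes.

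In Respiratory Hospitalization the ICD-10 run reads "J43.8', 'J43.9', 'J44.0', 'J45', 'J45.2", so it passes from J44.0 straight to J45. An admission with principal code J44.1 counts as an all-cause hospitalization but not as a respiratory one; an admission with principal code 491.21 counts as both. Lower Respiratory Infection under ICD-10 is only "J20.9”, “J21.0”, “J21.8”, “J22". The Charlson component ("If the event Chronic Obstructive Pulmonary Disease Occurs within 180 days, set the score to 1.0") scores every COPD event alike, so it cannot separate an exacerbation from stable disease.

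No diagnosis covariate therefore isolates an outpatient exacerbation. Under ICD-10 the codes are absent. Under ICD-9 they are pooled with the rest of 491 and need two claims at least 30 days apart.

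**How much baseline falls under ICD-9.** Assumption: claims switched to ICD-10 on 1 October 2015.

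*Primary cohort*
- Entry dates, 17 November 2015 to 31 March 2018: 866.
- The first entrant's baseline starts on 21 May 2015 and has 133 ICD-9 days, leaving 180 − 133 = 47 under ICD-10. Each later entry date loses one ICD-9 day, and the last affected date is 28 March 2016.
- Affected dates: 133/866 = 15.4%. Wholly ICD-9: none.
- ICD-9 share of baseline days, with entry uniform over time: (133 × 134/2)/(180 × 866) = 8,911/155,880 = 5.7%.
- Two claims at least 30 days apart need at least 31 days. The 30 entry dates with 30 or fewer ICD-9 days cannot qualify on two ICD-9 outpatient claims, which leaves 103.

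*Sensitivity analysis 3*
- Entry dates from 21 May 2015: 1,046.
- Wholly ICD-9 baselines: entries from 21 May to 1 October 2015, 134 dates. Mixed: 179 dates. Total 313/1,046 = 29.9%.
- ICD-9 share of baseline days: (134 × 180 + 179 × 180/2)/(180 × 1,046) = 40,230/188,280 = 21.4%.

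*Range for the assumed switch date*

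| Switch | Primary, any ICD-9 | Sensitivity 3, any ICD-9 |
|---|---|---|
| 1 Jul 2015 | 41 (4.7%) | 221 (21.1%) |
| 1 Oct 2015 | 133 (15.4%) | 313 (29.9%) |
| 1 Jan 2016 | 225 (26.0%) | 405 (38.7%) |

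**Does year of entry absorb it?** The first level runs from 17 November 2015 to 30 November 2016, which is 380 dates. Of these, 133 (35%) have mixed baselines and 247 are wholly ICD-10, so the level does not separate them.

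**The case against.** Several points against the concern are sound.

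- **The claim rule.** A reader might infer that a single outpatient exacerbation is counted under ICD-9 and lost under ICD-10. It is not counted in either: one outpatient 491.21 claim is also negative. The change from positive to negative applies to an inpatient claim or to two spaced outpatient claims. ICD-10 therefore did not remove an outpatient exacerbation measure that the plan once had.
- **Timing.** In the primary cohort the ICD-9 days are always the oldest part of the baseline, and about 85% of entry dates have none.
- **Share of positives.** It is tempting to state what fraction of Chronic Bronchitis positives come from 491.20–491.22. That needs prevalences the documents do not give, and scaling by ICD-9 days ignores the two-claim rule. No such figure is supportable.
- **Bias.** A reader might infer that the matched hazard ratio is biased. The same lists apply to both products, and bias from the era mismatch would need the product mix to shift with coding era within the affected months. The documents give nothing on that.
- **Code meanings.** Annex 4 does not say what the individual codes mean, and section 9.2.2 pairs the two systems as blocks, not code by code.
- **Existing safeguards.** Oral corticosteroids, oral antibiotics, short-acting bronchodilators, oxygen and emergency visits are covariates. Section 9.12 provides for medical review of code lists, and section 9.9 acknowledges residual confounding.

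These limit the size of the point but do not remove it. The fills and visits are indirect proxies, and none of the safeguards explains why one named covariate has two scopes or why Respiratory Hospitalization omits J44.1 and J44.9.

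**Conclusion.** The inconsistency is real and can be read directly from Annex 4 and section 9.2.2. Its early/late effect is modest in the primary cohort (15% of entry dates and 5.7% of baseline days) and larger in sensitivity analysis 3 (30% and 21%, with 134 entry dates wholly ICD-9). These figures rest on the assumed switch date and, for baseline days, on uniform entry.

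The more important conclusion needs neither assumption: no diagnosis covariate represents outpatient COPD exacerbation in either era, and the ICD-10 list for respiratory admissions omits J44.1 and J44.9. It does rest on reading 491.21, 491.22, J44.0 and J44.1 as the exacerbation or acute-infection codes, which the documents do not spell out.

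The direction and size of any effect on the hazard ratio are unknown. The change is worth making because it is cheap and the matched analysis has no later adjustment, not because a distortion has been shown.

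**What to change.** 1. **Chronic Bronchitis (Annex 4).** Give it the same scope in both systems, for example 491.0, 491.1, 491.8 and 491.9 with J41/J42.
2. **Respiratory Hospitalization (Annex 4).** Add J44.1 and J44.9 to the ICD-10 list, to match 491.21 and 496 on the ICD-9 side.
3. **New baseline covariate, COPD exacerbation.** Build it from 491.21, 491.22, J44.0 and J44.1. Add it to section 9.3.3, the propensity score, the multivariable models and Tables 2 and 3. State the claim-count rule: one inpatient or one outpatient claim, as Annex 4 already uses for acute myocardial infarction and cardiac arrhythmias. State the diagnosis position too, since those two measures use the principal or first position. If the covariate is not added, give the reason.

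Section 9.8 already allows measure definitions to be modified, with changes documented by amendment. The cost is an Annex 4 edit, one more covariate from data already held, and fewer patients labelled as having chronic bronchitis in Table 2.
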